8.8 Recording and Reporting of Adverse Events

The site Investigator is responsible for monitoring the safety of participants enrolled into the study at the study sites. For this study, non-serious AEs will not be collected on the safety reporting page of the CRF, but should be documented in the source documents and followed according to local standard of care.

SAEs, except for those anticipated AEs listed above, occurring from *signed informed consent* to Week 5 visit will be captured on the SAE CRF. Unless exempted as described above, all SAEs, whether or not deemed drug-related or expected, must be reported by the investigator or qualified designee within 1 working day of first becoming aware of the event. The investigator or qualified designee will enter the required information regarding the SAE into the appropriate CRF, which will be distributed to the appropriate sponsor contact.

Information collected on the adverse event worksheet (and entered in the research database):

- Subject's name:
- Medical record number:
- Disease/histology (if applicable):
- The date the adverse event occurred:
- Description of the adverse event:
- Relationship of the adverse event to the research (drug, procedure, or intervention):
- If the adverse event was expected:
- The severity of the adverse event: (use a table to define severity scale 1-5)
- If any intervention was necessary:

- Resolution: (was the incident resolved spontaneously, or after discontinuing treatment)
- Date of Resolution

8.2.7 Follow-up

When additional relevant information becomes available, the Investigator will record follow-up information according to the same process used for reporting the initial event as described above. The Investigator will follow all reportable events until resolution, stabilization or the event is otherwise explained. Investigators are also responsible for promptly reporting AEs to their reviewing IRB/EC in accordance with local requirements.

8.2.8 Suspected Unexpected Serious Adverse Reaction

AEs that meet the criteria of serious, related to study drug, and unexpected for that drug, qualify for expedited reporting to the regulatory authorities. The Site Investigator will assess all SAEs occurring at his/her site and evaluate for “unexpectedness” and relationship to study drug. The Site Investigator is required to complete and submit a voluntary MedWatch Report for the events identified as serious, study drug related and unexpected at:

<https://www.accessdata.fda.gov/scripts/medwatch/>. A copy of this report should be kept at the site and also forwarded to the overall study PI within the same timeline used for reporting to regulatory authorities.

8.2.9 Pregnancy

Pregnancy occurring during the study period, although not considered a serious adverse event, must be reported within the same timelines as a serious adverse event. The pregnancy will be recorded on the appropriate pregnancy form. The pregnancy will be followed until final outcome. Any associated AEs or SAEs that occur to the mother or fetus/child will be recorded in the AE or SAE CRF.

8.9 Stopping Rules

The study would be stopped only if advised because of unanticipated adverse events.

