8.7 Expectedness

The expectedness of an AE or SAR shall be determined according to the specified reference document containing safety information (e.g., most current product label). Any AE that is not identified in nature, severity, or specificity in the current study drug reference document(s) is considered unexpected. Events that are mentioned in the product label as occurring with a class

of drugs or as anticipated from the pharmacological properties of the drug, but not specifically mentioned as occurring with the particular drug under investigation are considered unexpected.

Anticipated Adverse Events and Procedure Effects

The following are anticipated, disease-related events in patients with HF or anticipated events of interest in patients with HFpEF taking Entresto™:

- **Arrhythmias:** This refers to both atrial and ventricular arrhythmias.
- **Acute coronary syndrome:** This refers to unstable angina, non ST segment elevation myocardial infarction (NSTEMI), and ST segment elevation myocardial (STEMI).
- **Unplanned hospitalization, ER visit or clinic visit for worsening HF:** This refers to treatment for acute heart failure such as receiving intravenous diuretics.
- **Cerebrovascular event:** This refers to cerebrovascular accidents (stroke) of any cause (hemorrhagic, ischemic, or embolic) and transient ischemic attack (TIA).
- **Venous thromboembolism:** This includes both deep venous thrombosis and pulmonary embolus.
- **Worsening renal function:** This refers to acute kidney injury, typically defined as an increase in eGFR \geq 20% over 48 hours, or progressive loss of renal function over time.
- **LVAD implantation:** This refers to implantation of a temporary or durable LVAD.
- **Cardiac Transplantation**
- **Hyperkalemia > 6 mEq/L**
- **Acute renal failure with serum creatinine > 2.5 mg/dL**
- **Angioedema**
- **Symptomatic hypotension**

Anticipated disease related events will not be captured as AEs/SAEs during the study, but will be entered on the appropriate case report form ("Events of Interest" page).

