8.10 Medical Monitoring

It is the responsibility of the Principal Investigator to oversee the safety of the study at his/her site. This safety monitoring will include careful assessment and appropriate reporting of adverse events as noted above, as well as the construction and implementation of a site data and safety-monitoring plan. Medical monitoring will include a regular assessment of the number and type of serious adverse events. After informal discussions with IRB staff in the midst of the study, given that 1. This was not a Phase 1,2,,3 study or clinical trial providing definitive information about effectiveness or safety of the drug 2. Prior data suggesting that the drug was safe to use leading to FDA approval for its use in heart failure 3. No major clinical endpoints were being evaluated to assess safety and effectiveness 4. No ethical issues were being raised in this proof of concept study regarding efficacy or safety that would lead to premature stopping of the study - a decision was made not to engage a DSMB.

9 Data Handling and Record Keeping

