9.3 Case Report Forms

The study case report form (CRF) is the primary data collection instrument for the study. All data requested on the CRF must be recorded. All missing data must be explained. If a space on the CRF is left blank because the procedure was not done or the question was not asked, write "N/D". If the item is not applicable to the individual case, write "N/A". All entries should be printed legibly in black ink. If any entry error has been made, to correct such an error, draw a single straight line through the incorrect entry and enter the correct data above it. All such changes must be initialed and dated. Do not erase or use "white-out" for errors. For clarification of illegible or uncertain entries, print the clarification above the item, then initial and date it. If the reason for the correction is not clear or needs additional explanation, neatly include the details to justify the correction. Study CRF components will include an enrollment and demographics form; forms for recording relevant history, HF symptoms, physical exam results, laboratory results, and other baseline presenting characteristics; follow-up forms for use during regular follow-up visits; forms to track the participant's clinical course over time; and event forms for recording the circumstances and details surrounding the occurrence of a death or hospitalization.

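### Section 8.9 lets the study stop only for undefined unanticipated adverse events, so on its plain reading an excess of four known drug risks listed as anticipated in 8.7 is not a ground to stop, and 8.8 read literally exempts those four from SAE reporting

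*Combined protocol and SAP*

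**What the plan says.** - **Stopping (8.9).** The whole rule is one sentence: "The study would be stopped only if advised because of unanticipated adverse events". It names no adviser, sets no threshold, does not mention pausing and does not define the term.
- **Anticipated events (8.7).** The list has 12 items. Its lead-in covers two classes, events related to the disease and "anticipated events of interest in patients with HFpEF taking Entresto™", but does not mark which item belongs to which class. Angioedema, symptomatic hypotension, hyperkalemia above 6 mEq/L and acute renal failure with creatinine above 2.5 mg/dL are all on it.
- **Capture under 8.7.** "Anticipated disease related events will not be captured as AEs/SAEs during the study"; they go to the Events of Interest page of the CRF instead.
- **Capture under 8.8.** The SAE form takes "SAEs, except for those anticipated AEs listed above". On timing: "Unless exempted as described above, all SAEs, whether or not deemed drug-related or expected, must be reported", within one working day.
- **Review (8.10).** "Medical monitoring will include a regular assessment of the number and type of serious adverse events". The Principal Investigator oversees safety, and 8.10 explains why no DSMB was engaged.
- **Known risks (7.1).** Angioedema, hypotension, hyperkalemia and renal failure are named as risks of the drug, along with cough and dizziness.

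**The concern.** The drug is used off label in HFpEF (1.3). The harms most foreseeable from its label are the ones that 8.7 classes as anticipated, and 8.9 confines a study stop to events that are not anticipated. If the team follows 8.9 as it reads, a run of angioedema or symptomatic hypotension well above what was foreseen gives no stated reason to stop.

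The reporting rules add to this. If staff follow 8.8 to the letter, a serious case of angioedema goes to the Events of Interest page rather than the SAE form, and no sentence says that this page is reviewed cumulatively across subjects. What is at stake is study-level safety oversight while subjects are being dosed. The biomarker comparison is not touched.

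**Working it through.** Section 8.9 states no rate or error probability, so there is no figure of the plan to reproduce. The check is mainly one of wording.

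**Step 1: match the lists.** Of the 12 items in 8.7, four correspond to reactions in 7.1: angioedema, hypotension (listed as symptomatic), hyperkalemia (listed above 6 mEq/L) and renal failure (listed above creatinine 2.5 mg/dL). Worsening renal function is also listed and overlaps with the last.

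**Step 2: test the readings of the undefined term in 8.9.**
- *Not on the anticipated list.* This is the plain reading. All four fall outside the rule, whatever their number.
- *Unexpected, as 8.7 defines it.* That definition turns on nature, severity or specificity against the label. A listed event more severe than labelled could then count. Frequency is not part of the definition, so an excess in number still does not.
- *An unforeseen number of cases.* This can be argued, but nothing in 8.9 settles it.

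**Step 3: compare the exemptions.** The exclusion in 8.7 names disease-related events and is silent on the drug-related items. The exemption in 8.8 covers everything listed. Both can be obeyed at once. Taken literally, the wider one governs SAE capture and one-day reporting.

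**Step 4: scale, as illustration only.** Inputs: n = 40 (7.1 Sample Size Determination). From 7.1 Summary of the Risks and Benefits: angioedema 0.5%, or 2.4% in Black patients; symptomatic hypotension 18%. That last sentence attributes an enalapril comparison to PARAGON, whereas 1.2 says PARAGON-HF compares with valsartan, so the source of the 18% is uncertain. The documents do not give the exposure time behind these rates, and they may be too high for five weeks. Halved rates are therefore shown as an assumption.

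With X ~ Binomial(40, p), the expected count is 40p and P(X ≥ 2) = 1 − (1 − p)^40 − 40p(1 − p)^39. For p = 0.005 this is 1 − 0.8183 − 0.1645 = 0.0172. The other rows use the same distribution.

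| Event | p | Expected | Tail probability |
|---|---|---|---|
| Angioedema | 0.5% | 0.2 | P(≥2) = 1.7% |
| Angioedema, half rate (assumed) | 0.25% | 0.1 | P(≥2) = 0.5% |
| Angioedema, all at the higher rate | 2.4% | 0.96 | P(≥2) = 25% |
| Symptomatic hypotension | 18% | 7.2 | P(≥13) = 2.0% |
| Symptomatic hypotension, half rate (assumed) | 9% | 3.6 | P(≥8) = 2.4% |

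If the true hypotension rate were 36% (an assumed doubling of 18%), 13 or more cases would have probability 73%. An excess could therefore be visible even with 40 subjects.

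**The case against.** The strongest reply is that this is a 40-subject, five-week study of a drug approved for heart failure, and that several other protections exist. The drug can be stopped in an individual subject (4.5, 7.1). The sentence in 8.10 before the SAE review sets a general duty to assess and report adverse events, not only serious ones. Section 8.2.8 has the Site Investigator assess all SAEs at the site, and that duty is not tied to the SAE form. Section 8.2.7 adds: "Investigators are also responsible for promptly reporting AEs to their reviewing IRB/EC in accordance with local requirements". Section 9.3 provides "event forms for recording the circumstances and details surrounding the occurrence of a death or hospitalization". All of this stands and softens the concern. None of it gives a study-level ground to stop for an excess of listed events, and none says that the Events of Interest page is reviewed in aggregate.

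Three stronger readings are tempting, and the documents do not support them:
- *That 8.7 and 8.8 contradict each other.* No sentence says the four drug-related items are captured as SAEs. The name of the Events of Interest page even suggests that 8.7 may have meant the whole list.
- *That serious listed events go unrecorded or unreviewed.* They are recorded on a CRF page, and 8.10 does not say that its review draws on SAE forms alone. It is silent on the source.
- *That 8.9 shuts out these four risks in every form.* An event more severe than labelled may still qualify, and hyperkalemia and acute renal failure are listed only above stated thresholds.

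It is also fair to say that the probabilities depend on the rates chosen: two angioedema cases range from 0.5% to 25%. They cannot serve as thresholds.

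**Conclusion.** The concern holds in a limited form. The sole stated stopping rule is exclusive and, on its plain reading, leaves out an excess in frequency of four known drug risks. Substituting the defined term *unexpected* does not repair this. Section 8.8 read literally also takes serious cases of the four out of SAE capture and one-day reporting, with partial mitigation elsewhere.

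In size, 4 of the 12 listed events are involved. At the rates shown, about 2 angioedema cases or 8 to 13 symptomatic hypotension cases would be unusual without giving a ground to stop under 8.9. If all subjects had the 2.4% rate, two angioedema cases would not be unusual. This rests on the plain reading of 8.9, and the counts rest on carrying the 7.1 rates over to this population and exposure. Confidence is medium because the key term is undefined. It is a cheap improvement to safety oversight, with no bearing on the primary result.

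**What to change.** - **8.9:** strike *only* and *unanticipated*. State that the study may be paused or stopped, on the advice of the overall study PI or the IRB, because of any pattern of adverse events, including those listed in 8.7.
- **8.10:** add the cumulative Events of Interest, pooled over all subjects, to the regular assessment.
- **8.8:** limit the exemption to the disease-related items and name them, so that serious angioedema, symptomatic hypotension, hyperkalemia and acute renal failure are reported as SAEs. The sponsor should say on which side worsening renal function falls.

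Any numerical trigger is for the sponsor to choose.

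The cost is one protocol amendment with IRB approval (8.1, 11.2), one more pooled table per review from data already on the CRF, and a few more SAE reports. No DSMB or new study procedure is needed. The downsides are that the study could be paused for a known risk and that the decision stays discretionary. One limit remains: the schedule of events has potassium and creatinine at screening only, so hyperkalemia and renal failure after dosing will appear only if found clinically.

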8.10 Medical Monitoring

It is the responsibility of the Principal Investigator to oversee the safety of the study at his/her site. This safety monitoring will include careful assessment and appropriate reporting of adverse events as noted above, as well as the construction and implementation of a site data and safety-monitoring plan. Medical monitoring will include a regular assessment of the number and type of serious adverse events. After informal discussions with IRB staff in the midst of the study, given that 1. This was not a Phase 1,2,,3 study or clinical trial providing definitive information about effectiveness or safety of the drug 2. Prior data suggesting that the drug was safe to use leading to FDA approval for its use in heart failure 3. No major clinical endpoints were being evaluated to assess safety and effectiveness 4. No ethical issues were being raised in this proof of concept study regarding efficacy or safety that would lead to premature stopping of the study - a decision was made not to engage a DSMB.

9 Data Handling and Record Keeping

9.1 Confidentiality

Information about study subjects will be kept confidential and managed according to the requirements of the Health Insurance Portability and Accountability Act of 1996 (HIPAA). Those regulations require a signed subject authorization informing the subject of the following:

- What protected health information (PHI) will be collected from subjects in this study

- Who will have access to that information and why
- Who will use or disclose that information
- The rights of a research subject to revoke their authorization for use of their PHI.

In the event that a subject revokes authorization to collect or use PHI, the investigator, by regulation, retains the ability to use all information collected prior to the revocation of subject authorization. For subjects that have revoked authorization to collect or use PHI, attempts should be made to obtain permission to collect at least vital status (long term survival status that the subject is alive) at the end of their scheduled study period.

9.2 Source Documents

Source data is all information, original records of clinical findings, observations, or other activities in a clinical trial necessary for the reconstruction and evaluation of the trial. Source data are contained in source documents. Examples of these original documents, and data records include: hospital records, clinical and office charts, laboratory notes, memoranda, subjects' diaries or evaluation checklists, pharmacy dispensing records, recorded data from automated instruments, copies or transcriptions certified after verification as being accurate and complete, microfiches, photographic negatives, microfilm or magnetic media, x-rays, subject files, and records kept at the pharmacy, at the laboratories, and at medico-technical departments involved in the clinical trial.

9.3 Case Report Forms

The study case report form (CRF) is the primary data collection instrument for the study. All data requested on the CRF must be recorded. All missing data must be explained. If a space on the CRF is left blank because the procedure was not done or the question was not asked, write "N/D". If the item is not applicable to the individual case, write "N/A". All entries should be printed legibly in black ink. If any entry error has been made, to correct such an error, draw a single straight line through the incorrect entry and enter the correct data above it. All such changes must be initialed and dated. Do not erase or use "white-out" for errors. For clarification of illegible or uncertain entries, print the clarification above the item, then initial and date it. If the reason for the correction is not clear or needs additional explanation, neatly include the details to justify the correction. Study CRF components will include an enrollment and demographics form; forms for recording relevant history, HF symptoms, physical exam results, laboratory results, and other baseline presenting characteristics; follow-up forms for use during regular follow-up visits; forms to track the participant's clinical course over time; and event forms for recording the circumstances and details surrounding the occurrence of a death or hospitalization.

9.4 Data Quality Control

Prior to the start of enrollment, the Investigators and Study Coordinators will be trained on the clinical protocol and data collection procedures. Personnel at the clinical sites will enter the data mandated by the protocol into the CRFs. The data will be extracted from the participant's medical charts and other source documents. All CRFs will be completed according to the current Good Clinical Practice (GCP) guidelines. Follow-up training and training for new study personnel will be conducted as needed.

9.5 Data Security

Access to databases will be controlled centrally through user passwords linked to appropriate privileges. This protects the data from unauthorized changes and inadvertent loss or damage. Database and web servers will be secured by a firewall and through controlled physical access.

Database back-up will be performed daily using standard procedures. All disk drives that provide network services, and all user computers, will be protected using virus-scanning software.

9.6 Publication Policy

Dissemination of preliminary information can adversely affect the objectivity of study data. For this reason, Investigators will be prohibited from performing subset analyses at any point prior to the conclusion of the study, and any data, other than safety data, cannot be used for publication or reporting outside of this study until the study is completed.

10 Study Monitoring, Auditing, and Inspecting

10.1 Study Monitoring Plan

The investigator will allocate adequate time for such monitoring activities. The investigator will also ensure that the monitor or other compliance or quality assurance reviewer is given access to all the study-related documents and study related facilities (e.g. pharmacy, diagnostic laboratory, etc.), and has adequate space to conduct the monitoring visit.

10.2 Auditing and Inspecting

The investigator will permit study-related monitoring, audits, and inspections by the IRB, and government regulatory agencies, of all study related documents (e.g. source documents, regulatory documents, data collection instruments, study data etc.). The investigator will ensure the capability for inspections of applicable study-related facilities (e.g. pharmacy, diagnostic laboratory, etc.). Participation as an investigator in this study implies acceptance of potential inspection by government regulatory authorities and applicable compliance offices.

11 Regulatory Issues

11.1 Ethics and Good Clinical Practice

This study must be carried out in compliance with the protocol and in accordance with DCRI standard operating procedures. These procedures are designed to ensure adherence to Good Clinical Practice, as described in the following documents:

1. ICH Harmonized Tripartite Guidelines for Good Clinical Practice 1996.
2. US 21 Code of Federal Regulations dealing with clinical studies (including parts 50 and 56 concerning informed consent and IRB regulations).
3. Declaration of Helsinki, concerning medical research in humans (Recommendations Guiding Physicians in Biomedical Research Involving Human Subjects, Helsinki 1964, amended Tokyo 1975, Venice 1983, Hong Kong 1989, Somerset West 1996).

By signing the protocol, the investigator agrees to adhere to the instructions and procedures described in it and thereby to adhere to the principles of Good Clinical Practice to which it conforms.

